5.8 Duration of Follow Up

Participants will be followed for 30 days after last dose of study drug. Patients who are not hospitalized at the time of follow up will be seen in the outpatient clinic. Participants removed from protocol therapy for unacceptable adverse event(s) will be followed until resolution or stabilization of the adverse event.

5.9 Criteria for Taking a Participant Off Study

Participants will be removed from study when any of the following criteria apply:

- Lost to follow-up
- Withdrawal of consent for data submission
- Death

The reason for taking a participant off study, and the date the participant was removed, must be documented in the case report form (CRF). In addition, the study team will ensure Off Treatment/Off Study information is updated in OnCore in accordance with DF/HCC policy REGIST-101.

5.10 Early Withdraw

Any patient who is enrolled in the study, but withdraws prematurely at any time for any reason before the end of their Day 30 follow-up visit (or phone call) for isolated HIT or Day 90 follow up visit (or phone call) for HITT, is considered an early withdraw and will not be replaced. A

complete set of data including the reason for the early withdraw will be collected on each patient through the time of withdraw. Every effort will be made to ascertain patient safety and survival information at the Day 30 follow-up time-point for isolated HIT and Day 90 for HITT.

Note: Date of follow up refers to the total days since initiation of treatment.

6 DOSING CHANGES

Dose changes will be made as indicated in the following table(s). The descriptions and grading scales found in the revised NCI Common Terminology Criteria for Adverse Events (CTCAE) version 4.0 will be utilized for dose changes. A copy of the CTCAE version 4.0 can be downloaded from the CTEP website

http://ctep.cancer.gov/protocolDevelopment/electronic_applications/ctc.htm.

Bleeding	Management of Patient	Management Of Apixaban
≤ Grade 1	Mild, intervention not indicated	Continue apixaban and monitor closely
Grade 2	Symptomatic and medical intervention indicated	Stop apixaban, take off protocol
Grade 3	Transfusion, interventional radiology, endoscopic, or operative intervention indicated; radiation therapy (i.e., hemostasis of bleeding site)	Stop apixaban, take off protocol
Grade 4	Life-threatening consequences; major urgent intervention indicated	Stop apixaban, take off protocol
Grade 5	Death	Stop apixaban, take off protocol

Apixaban will also be stopped and patient will be taken off protocol for any major bleed. Decisions regarding further treatment for patients who experience a major hemorrhagic event will be deferred to the primary team. They will be followed to the end of the study in an intention-to-treat analysis.

Major bleeding is defined as overt bleeding and:

- associated with a decrease in hemoglobin of ≥ 2 g/dL, or
- leading to a transfusion of ≥ 2 units of packed red blood cells or whole blood, or
- occurring in a critical site: intracranial, intraspinal, intraocular, pericardial, intra-articular, intramuscular with compartment syndrome, retroperitoneal, or
- contributing to death.

6.1 Reversal of Anticoagulation Effect

A specific antidote for Apixaban is not available, and there is no established way to reverse bleeding in patients taking Apixaban. The pharmacodynamic effect of APIXABAN can be

expected to persist for at least 24 hours after the last dose, i.e., for about two drug half-lives. Use of procoagulant reversal agents, such as prothrombin complex concentrate (PCC), activated prothrombin complex concentrate or recombinant factor VIIa, has not been evaluated in clinical studies. Activated oral charcoal reduces absorption of apixaban, thereby lowering apixaban plasma concentration [see *Overdosage below*]. Hemodialysis does not appear to have a substantial impact on apixaban exposure. Protamine sulfate and vitamin K are not expected to affect the anticoagulant activity of apixaban. There is no experience with antifibrinolytic agents (tranexamic acid, aminocaproic acid) in individuals receiving apixaban. There is no experience with systemic hemostatic agents (desmopressin and aprotinin) in individuals receiving apixaban and they are not expected to be effective as a reversal agent.

Because there is no specific antidote to reverse the effect of apixaban, the following steps are recommended for subjects with ongoing life-threatening bleeding (bleeding resulting in hemodynamic compromise requiring intervention or any intracranial hemorrhage):

- Withhold study drug and all antiplatelets/anticoagulants;
- Institute standard of care for life-threatening bleeding (large bore IV or central venous line, type and crossmatch blood, admit to the intensive care unit, provide hemodynamic and respiratory support);
- Administer packed red blood cells (or whole blood) as needed.

If life-threatening bleeding persists, it is recommended to contact the PI to discuss subject management.

6.2 Overdose

There is no antidote to Apixaban. Overdose of Apixaban increases the risk of bleeding. In controlled clinical trials, orally administered apixaban in healthy subjects at doses up to 50 mg daily for 3 to 7 days (25 mg twice daily for 7 days or 50 mg once daily for 3 days) had no clinically relevant adverse effects.

In healthy subjects, administration of activated charcoal 2 and 6 hours after ingestion of a 20-mg dose of apixaban reduced mean apixaban AUC by 50% and 27%, respectively. Thus, administration of activated charcoal may be useful in the management of apixaban overdose or accidental ingestion.

7 ADVERSE EVENTS: LIST AND REPORTING REQUIREMENTS

An Adverse Event (AE) is defined as any new untoward medical occurrence or worsening of a preexisting medical condition in a clinical investigation participant administered study drug and that does not necessarily have a causal relationship with this treatment. An AE can therefore be any unfavorable and unintended sign (such as an abnormal laboratory finding), symptom, or disease temporally associated with the use of investigational product, whether or not considered related to the investigational product.

The causal relationship to study drug is determined by a physician and should be used to assess all adverse events (AE).

Adverse events can be spontaneously reported or elicited during open-ended questioning, examination, or evaluation of a subject. (In order to prevent reporting bias, subjects should not be questioned regarding the specific occurrence of one or more AEs.)

An abnormal laboratory value will not be assessed as an AE unless that value leads to discontinuation or delay in treatment, dose modification, therapeutic intervention, meets the definition of an SAE or AESI, or is considered by the investigator to be a clinically significant change from baseline.

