The patient will be assessed on Day 30 (\pm 5 days) from initiation of therapy, preferably in clinic. If clinic follow up is feasible, all of the following data must be recorded. If patient is unable to come to clinic (ie due to living in another city or unable to travel), day 30 follow up can be completed by telephone interview and the labs, exam and vitals will not be recorded.

The following data must be recorded:

- Summary of patient's clinical course
- Any adverse events that occurred between Day of Discharge through Day 30 including signs and symptoms of TEC.
- CBC, chemistries, coagulation profile*
- Physical exam and vital signs*
- Concomitant Medications
- For patients discharged on apixaban:
 - Retrieve study medication and diary
 - Record the stop date of discontinuation of apixaban.

**unable to obtain if follow up is telephone interview*

5.3.6 **Follow-up for patients with HITT: Day 90 (+/- 5 days)**

The patient will be assessed on Day 90 (± 5 days), from initiation of therapy, preferably in clinic. If clinic follow up is feasible, all of the following data must be recorded. If patient is unable to come to clinic (ie due to living in another city or unable to travel), day 90 follow up can be completed by telephone interview and the labs, exam and vitals will not be recorded.

The following data must be recorded:

- Summary of patient's clinical course
- Any adverse events that occurred between Day of Discharge through Day 90 including signs and symptoms of TEC.
- CBC, chemistries, coagulation profile*
- Physical exam and vital signs*
- Concomitant Medications
- For patients discharged on apixaban:
 - Retrieve study medication and diary
 - Record the stop date of discontinuation of apixaban.

**unable to obtain if follow up is telephone interview*

5.3.7 **Follow-up 30 days after last dose of therapy (+/- 5 days)**

The patient will be assessed on 30 days (± 5 days), after last dose of therapy. If clinic follow up is feasible, all of the following data must be recorded. If patient is unable to come to clinic (ie due to living in another city or unable to travel), this follow up can be completed by telephone interview and the labs, exam and vitals will not be recorded.

The following data must be recorded:

- Summary of patient's clinical course
- Any adverse events through 30 days after the last dose of therapy including signs and symptoms of TEC.
- CBC, chemistries*
- Physical exam and vital signs*
- Concomitant Medications

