11.1.2 Safety

Monitoring of adverse events will be conducted throughout the study, and include new or subsequent TEC, major bleeding (in particular fatal, life-threatening, disabling, requiring a surgical intervention), further thrombocytopenia, disseminated intravascular coagulopathy, skin necrosis, allergic reaction or other events which in the opinion of the investigator are related to anticoagulation therapy. New adverse events, including serious adverse events, will be captured on the CRFs including through 30 days after enrollment for isolated HIT and 90 days after enrollment for HITT as well as 30 days after discontinuation of all treatment. New-onset adverse events and serious adverse events should be monitored until they are resolved or are clearly determined to derive from a patient's stable or chronic condition or intercurrent illness(es). Definitions, documentation, and reporting of adverse events are described in section 7.

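### Section 7's rule against asking about specific adverse events conflicts with collecting new TEC, the primary endpoint, and bleeding at a Day-30 contact that may be by telephone

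*Combined protocol and SAP*

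**What the plan says.** **Eliciting adverse events.** Section 7 states: "Adverse events can be spontaneously reported or elicited during open-ended questioning, examination, or evaluation of a subject". It adds in parentheses, to prevent reporting bias, that "subjects should not be questioned regarding the specific occurrence of one or more AEs". No endpoint is exempted.

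**What counts as an adverse event.** Section 11.1.2: "Monitoring of adverse events will be conducted throughout the study, and include new or subsequent TEC, major bleeding".

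**Day 30.** Section 5.3.5 prefers a clinic visit, but if the patient cannot attend, "day 30 follow up can be completed by telephone interview and the labs, exam and vitals will not be recorded". The items to record include "Any adverse events that occurred between Day of Discharge through Day 30 including signs and symptoms of TEC".

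**TEC assessment.** Section 5.3.9 requires evaluation for thrombosis at every visit. The calendar in Section 10 has a row for TEC signs and symptoms, separate from the adverse-event row, marked at every contact. Its footnote 11 allows a telephone call instead of a follow-up clinic visit.

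**Withdrawals.** Under Section 5.10 a patient who leaves before the Day-30 contact (Day 90 for HITT) "is considered an early withdraw and will not be replaced", and "Every effort will be made to ascertain patient safety and survival information at the Day 30 follow-up time-point".

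**Success rule.** Section 13.1 declares success if at least 34 of 44 confirmed patients are alive without new TEC at Day 30. New TEC and death are the only failures named.

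**The concern.** The plan gives two instructions for collecting its primary endpoint, and they disagree. One tells staff to look for TEC at each contact. The other tells them not to ask about any particular adverse event, and TEC is collected as one.

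In clinic, examination can fill the gap. By telephone it cannot. A coordinator who follows Section 7 to the letter would ask how the patient has been, but not about leg swelling, chest pain or a clot treated elsewhere. Section 5.3.8 accepts that study procedures may be impossible when a patient is admitted to an outside hospital, so the patient's own account may be the first notice of such an event.

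The error runs one way. There is no control arm in which similar under-ascertainment could offset it, and every missed TEC in a patient recorded as alive moves the count toward 34. Major bleeding, a secondary endpoint, can be under-counted in the same way.

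**Working it through.** **1. The passages side by side**

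| Source | Instruction |
|---|---|
| Section 7 | Do not ask about specific adverse events; open questions, examination and evaluation allowed |
| Section 11.1.2 | New TEC and major bleeding are monitored as adverse events |
| Section 5.3.5 | Day-30 TEC signs and symptoms must be recorded; by telephone only laboratory tests, examination and vital signs are waived |
| Section 5.3.9 and calendar | Evaluate for TEC at each visit |

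The TEC item is not waived by telephone, but no passage says how to obtain it within Section 7's limits.

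**2. The plan's own figure.** The exact 90% lower bound for x successes in n is the 5% quantile of a Beta(x, n − x + 1) distribution. For 34/44 it is 0.6451, and the upper bound is 0.8712. This reproduces the stated 65% to 87%.

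**3. Sensitivity to one event.** For 33/44 the lower bound is 0.620, and for 34/44 it is 0.645. One missed TEC turns 33 recorded successes into 34, and so a failed trial into a declared success.

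**4. Illustration of missed TECs.** Inputs:
- n = 44 and cut-off 34, from Section 13.1.
- True success 0.65, the benchmark in Section 13.1.
- t, the share of patients with TEC. 7% is the argatroban figure in Section 13.1. 15% is an assumption; it lies between the 6–8% and the 25% quoted in Section 2.1.
- m, the share of TECs missed. This is an assumption, because the documents give no figure.

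Apparent success is p = 0.65 + t × m. The chance of declaring success is P(X ≥ 34) for X ~ Binomial(44, p).

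| t | m | p | Mean number missed (44 × t × m) | P(X ≥ 34) |
|---|---|---|---|---|
| any | 0 | 0.650 | 0 | 0.057 |
| 7% | 10% | 0.657 | 0.3 | 0.069 |
| 7% | 20% | 0.664 | 0.6 | 0.083 |
| 7% | 30% | 0.671 | 0.9 | 0.099 |
| 15% | 20% | 0.680 | 1.3 | 0.122 |
| 15% | 30% | 0.695 | 2.0 | 0.170 |

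The starting value is 0.057, above 0.05, because the bound of 0.6451 was rounded up to 0.65. That is separate from this point.

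**5. Unknown Day-30 status.** Suppose k of the 44 have unknown status and true success is 0.65. Counted as successes, the chance of declaring success is P(X ≥ 34 − k) with X ~ Binomial(44 − k, 0.65). Counted as not successes, it is P(X ≥ 34) with the same X. For k = 1 these are 0.070 and 0.034; for k = 2, 0.084 and 0.019. The documents do not say which applies.

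**The case against.** The strongest reply is that nothing blocks TEC ascertainment. The Section 7 sentence is a parenthetical *should not* about eliciting adverse events, and the same paragraph allows evaluation of the subject. TEC assessment is required separately by Sections 5.3.5 and 5.3.9 and the calendar. By telephone, the clinical-course summary, the concomitant medications and, for patients discharged on apixaban, its stop date are still collected, and any of these can reveal an event without a leading question. A countable deep vein thrombosis needs imaging confirmation (Section 11.1.1), so someone will already have diagnosed it. Section 2.3 puts the greatest TEC risk early, and inpatients are assessed daily. Later contacts, at Day 90 for HITT and 30 days after the last dose, record TEC again.

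Most of this stands. A reader might infer that Section 7 forbids finding TEC, but the documents support only a conflict to be reconciled. These safeguards also make the higher missed fractions less likely. They do not remove the conflict: none says that Section 7 yields, and none gives wording for the call. An outside diagnosis enters the count only if the study team learns of it.

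Section 5.10 invites two further inferences. The first is that the plan seeks nothing beyond survival and general safety for withdrawn patients. But Section 11.1.2, headed Safety, lists new TEC, so TEC is plausibly included, though it is not named. The second is that withdrawn patients are scored as successes or leave the denominator. No passage says either, and the per-protocol set in Section 13.6.2 removes only patients with negative confirmatory tests.

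**Conclusion.** The point holds as a conflict in how the primary endpoint and major bleeding are elicited. It is sharpest at a telephone contact, and its bias favours success. At a true success rate of 65%, the chance of declaring success moves from 0.057 to 0.069–0.099 at the plan's own 7% TEC rate with 10–30% of events missed. It reaches 0.12–0.17 if 15% have TEC and 20–30% are missed. These are illustrations. The missed fractions and the 15% rate are assumptions, and m applies to all TECs over 30 days, including those in hospital where detection should be good. What needs no assumption about frequency is that one missed TEC separates 33/44 from 34/44. The handling of unknown Day-30 status is a lesser matter: a rule is missing, and its direction cannot be read from the documents. The conflict should be corrected, but it does not by itself invalidate the design.

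**What to change.** **Main change, Section 7.** Exempt TEC and bleeding from the no-specific-questions sentence. Require a short fixed checklist covering TEC symptoms and diagnoses, bleeding, amputation and outside admissions. Use it at the Day-30, Day-90 and post-treatment contacts, in clinic or by telephone, and refer to it from Sections 5.3.5 to 5.3.7.

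**Secondary clarifications.**
- Section 5.10: name new TEC status in the Day-30 information sought for patients who withdraw.
- Section 13.1: state how an unknown Day-30 status is counted, for example as not a success.

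**Cost.** A few sentences and a one-page form. Visits, sample size and cut-off do not change. The downside is that slightly more solicited minor symptoms will be recorded. Counting unknowns as not successes makes the trial harder to pass: with two unknowns at a true rate of 65%, the chance of success is 0.019, against 0.057 with none.

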7.1 Nonserious Adverse Event

A nonserious adverse event is an AE not classified as serious.

- Nonserious Adverse Events are to be provided to BMS in aggregate via interim or final study reports as specified in the agreement or, if a regulatory requirement [e.g. IND US trial] as part of an annual reporting requirement.

7.1.1 Nonserious Adverse Event Collection and Reporting

The collection of nonserious AE information should begin following the subject's written consent to participate in the study. All nonserious adverse events (not only those deemed to be treatment-related) should be collected continuously during the treatment period and for a minimum of 30 days following the last dose of study treatment.

Nonserious AEs should be followed to resolution or stabilization, or reported as SAEs if they become serious. Follow-up is also required for nonserious AEs that cause interruption or discontinuation of study drug and for those present at the end of study treatment as appropriate. Nonserious Adverse Events are provided to BMS via annual safety reports (if applicable), and interim or final study reports.

7.2 Laboratory Test Abnormalities

All laboratory test results captured as part of the study should be recorded following institutional procedures. Test results that constitute SAEs should be documented and reported as such.

The following laboratory abnormalities should be documented and reported appropriately:

- any laboratory test result that is clinically significant or meets the definition of an SAE
- any laboratory abnormality that required the participant to have study drug discontinued or interrupted
- any laboratory abnormality that required the subject to receive specific corrective therapy.

It is expected that wherever possible, the clinical rather than laboratory term would be used by the reporting investigator (eg, anemia versus low hemoglobin value).

7.3 Serious Adverse Event

A Serious Adverse Event (SAE) is any untoward medical occurrence that at any dose:

- results in death
- is life-threatening (defined as an event in which the participant was at risk of death at the time of the event; it does not refer to an event which hypothetically might have caused death if it were more severe)
- requires inpatient hospitalization or causes prolongation of existing hospitalization (see **NOTE** below)
- results in persistent or significant disability/incapacity
- is a congenital anomaly/birth defect
- is an important medical event (defined as a medical event(s) that may not be immediately life-threatening or result in death or hospitalization but, based upon appropriate medical and scientific judgment, may jeopardize the subject or may require intervention [eg, medical, surgical] to prevent one of the other serious outcomes listed in the definition above.) Examples of such events include, but are not limited to, intensive treatment in an emergency room or at home for allergic bronchospasm; blood dyscrasias or convulsions that do not result in hospitalization.)
- Suspected transmission of an infectious agent (eg, pathogenic or nonpathogenic) via the study drug is an SAE.

Although pregnancy, overdose, potential drug-induced liver injury (DILI) and cancer are not always serious by regulatory definition, these events must be handled as SAEs.

Any component of a study endpoint that is considered related to study therapy should be reported as an SAE if it meets the above SAE definition (eg, death is an endpoint, if death occurred due to anaphylaxis, anaphylaxis must be reported).

NOTE: The following hospitalizations are not considered SAEs:

- a visit to the emergency room or other hospital department < 24 hours, that does not result in admission (unless considered an important medical or life-threatening event)
- elective surgery, planned prior to signing consent
- admissions as per protocol for a planned medical/surgical procedure
- routine health assessment requiring admission for baseline/trending of health status (eg, routine colonoscopy)
- Medical/surgical admission other than to remedy ill health and planned prior to entry into the study. Appropriate documentation is required in these cases
- Admission encountered for another life circumstance that carries no bearing on health status and requires no medical/surgical intervention (eg, lack of housing, economic inadequacy, caregiver respite, family circumstances, administrative reason).

7.4 Overdose

An overdose is defined as the accidental or intentional administration of any dose of a product that is considered both excessive and medically important. All occurrences of overdose must be reported as SAEs.

7.5 Other Safety Considerations

Any significant worsening noted during interim or final physical examinations, electrocardiograms, x-rays, and any other potential safety assessments, whether or not these procedures are required by the protocol, should also be recorded as a nonserious or serious adverse event, as appropriate, and reported accordingly.

